## 7 RESEARCH QUESTION AND OBJECTIVES

The objectives of the MARS are:

- 1. To characterize and describe the MPS IVA population as a whole, including the heterogeneity, progression, and natural history of MPS IVA.
- 2. To evaluate the long-term effectiveness and safety of Vimizim, including, but not limited to, the occurrence of serious hypersensitivity reactions, anaphylaxis, and changes in antibody status.
- 3. To help the medical community with the development of recommendations for monitoring MPS IVA patients and reports on patient outcomes to optimize patient care.
- 4. To collect data on other treatments and evaluate the prevalences of their use and their effectiveness.
- 5. To characterize the effects and safety of Vimizim treatment up to 5 years from enrolment in the Registry for patients under 5 years of age.
- 6. To monitor pregnancy exposure, including maternal, neonatal, and infant outcomes.
- 7. To monitor patients who have completed the MOR-005 and MOR-007 clinical trials. These patients will be encouraged to enroll in the applicable Registry Substudy and will be monitored using the MOR-005 and MOR-007 assessment schedules respectively.

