# 11.1 Timepoints

Among enzyme replacement therapy (ERT)-treated patients:

- Registry Entry is defined as at the date of patient signed consent to participate in MARS
- Index is defined as the date of first exposure to Vimizim (may precede or follow Registry Entry)
- Baseline is defined as within 12 months prior to index or within 1 month after index. Historic data prior to index collected with the data point closest to index in the 12 months prior to index or 1 month after index (except for measurement of urinary keratan sulfate [uKS]) is considered the baseline measurement
- Follow-up is defined as the time period after index plus 1 month (Index Date + 30 days +1) to last data point.

Among ERT-naive patients:

- Registry Entry is defined as at the date of patient signed consent to participate in MARS
- Follow-up is defined as the time period from Registry Entry (exclusive) to last data point

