# 18.1.5 Analysis Populations

# 18.1.5.1 Safety Population

The Safety Population will consist of all patients who receive at least 1 dose of Vimizim at or after registry entry.

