Long-term safety events occurring during MARS after index or registry entry (which ever occurs later), including hypersensitivity events, will be evaluated by summarising the incidences of AEs by System Organ Class, Preferred Term, relationship to Vimizim, and severity in the Safety Population. Exposure-adjusted incidence rates and event rates while on treatment will be included as part of long-term safety evaluation. All AE summaries will include only treatment-emergent adverse events (TEAEs) and SAEs reported during the study period (AEs that occur after the first Vimizim infusion). Analyses of AEs of hypersensitivity and anaphylaxis, and AEs temporally related to a Vimizim infusion will be summarised by System Organ Class, PT, and severity All AEs will be coded using the most recent version of Medical Dictionary for Regulatory Activities (MedDRA).

Total and neutralizing antibody status will be summarised over the follow-up period.

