# 23 PROCEDURES FOR COLLECTION, MANAGEMENT AND REPORTING OF AES/ARS

# 23.1 Adverse Event Reporting Period

The reporting period for AEs and SAEs described in Section 22 begins from the time informed consent is signed and continues throughout the patient's enrolment in the Registry.

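### The Objective 2 adverse event rates pool patients starting Vimizim with patients already on it at entry, so they describe risk after starting treatment only if the hazard is constant over time on drug

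*Protocol*

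**What the plan says.** Objective 2 (Protocol section 7) names "the occurrence of serious hypersensitivity reactions, anaphylaxis, and changes in antibody status" among the safety outcomes. Four provisions decide how they are counted.

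- **Population (18.1.5.1).** The Safety Population is "all patients who receive at least 1 dose of Vimizim at or after registry entry". It makes no distinction by when treatment began.
- **Event window (18.1.7, Objective 2).** The analysis covers "Long-term safety events occurring during MARS after index or registry entry (which ever occurs later), including hypersensitivity events". Section 11.1 defines index as first exposure and allows it to fall on either side of Registry Entry.
- **Reporting (23.1).** The adverse event reporting period "begins from the time informed consent is signed and continues throughout" the patient's time in the Registry.
- **Summaries (18.1.7, Objective 2).** "Exposure-adjusted incidence rates and event rates while on treatment will be included as part of long-term safety evaluation". For the reactions of interest: "Analyses of AEs of hypersensitivity and anaphylaxis, and AEs temporally related to a Vimizim infusion will be summarised by System Organ Class, PT, and severity". Neither time since first infusion nor treatment status at entry is among the dimensions named.

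Section 18.1.7 also provides separate Substudy analyses that combine MOR-005 Substudy data with the MOR-005 trial, and similarly for MOR-007. Objective 5 repeats the Objective 2 analyses for children whose index fell before age 5, over the 5 years after index.

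**The concern.** Two kinds of patient enter the same rate. A new starter is observed from the first infusion. A patient already treated at entry is observed only from some later point on drug. A patient who reacted early, stopped before entry and did not restart is not observed at all. This is left truncation with prevalent users.

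Such patients are part of the design. A patient in a BMN 110 trial may enrol only after completing or leaving it (3, 8.3.3), and Substudy patients must have completed MOR-005 or MOR-007 (8.3.2).

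If the hazard of hypersensitivity or anaphylaxis changes with time since first infusion, the pooled rate depends on how many patients of each kind happened to enrol. If the hazard is higher early, the rate is lower than a cohort followed from first infusion would show. A prescriber or regulator could take it as the risk facing a patient about to start. A single pooled figure could not show whether the hazard is constant.

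**Working it through.** The protocol states no sample size, event count or adverse event rate, so there is no figure of its own to reproduce. The size has to be illustrated under assumptions.

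**1. How many patients could enter already exposed (Table 6.1.1).** MOR-100 17, MOR-005 173, MOR-006 15, MOR-007 15, MOR-008 25, 110-502 13, 110-503 57:

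17 + 173 + 15 + 15 + 25 + 13 + 57 = 315.

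This is an upper bound assuming no overlap, not an enrolment count. MOR-005 and MOR-007 supply 173 + 15 = 188 of the 315 (60%). The other 127 have no trial data added back by the Substudy analyses, nor do patients who started outside these studies before entry.

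**2. Effect of pooling on the rate.** Assumptions, none from the documents:
- the hazard is *k* times the later hazard during the first 6 months, and the later hazard is set to 1;
- new starters are followed for 5 years from index;
- a share *p* of person-time comes from established users who are all past 6 months.

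New-user 5-year rate = (0.5*k* + 4.5)/5. Pooled rate = *p* × 1 + (1 − *p*) × new-user rate.

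| *k* | New-user rate | Pooled, *p* = 0.2 | Pooled, *p* = 0.8 | Pooled / new-user |
|---|---|---|---|---|
| 1 | 1.0 | 1.00 | 1.00 | 100% |
| 2 | 1.1 | 1.08 | 1.02 | 93-98% |
| 5 | 1.4 | 1.32 | 1.08 | 77-94% |
| 10 | 1.9 | 1.72 | 1.18 | 62-91% |

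For *k* of 5 to 10 the range is 62-94%.

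**3. Sensitivity to the length of the high-risk period.** Let the raised hazard last a full year, with new starters a share *s* of 0.1 to 0.5 and follow-up *F* of 3 to 8 years. With later hazard 1, the new-starter average is (*k* + *F* − 1)/*F*, and the pooled rate is *s* × that average + (1 − *s*). The new-starter average is then 1.06-1.29 times the pooled rate for *k* = 2, 1.2-2.1 times for *k* = 5 and 1.4-3.1 times for *k* = 10. The direction is the same; the size depends on the assumption.

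**4. Objective 5.** Five years is about 261 weeks. A MOR-007 patient treated for the full 209 weeks before entry has at most 261 − 209 = 52 weeks left in which Registry events can be counted, and they are the last 52.

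**5. Person-time.** The text fixes when events start to count but not when person-time does. If person-time ran from index while events ran from entry, a constant true rate would be multiplied by *F*/(*F* + (1 − *s*)*P*), where *P* is years of prior exposure. With *P* from 1 to 4.6 years (240 weeks in MOR-005 is about 4.6 years), *F* of 5 or 8 and *s* of 0.1 to 0.5, the factor runs from 5/(5 + 0.9 × 4.6) = 0.55 to 8/(8 + 0.5 × 1) = 0.94. The protocol does not say this will be done; one sentence would exclude it.

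**The case against.** **The window is correct, and that stands.** A reader might infer that leaving out pre-entry time is itself an error. It is not. Adverse events are reported only from consent, so adding earlier person-time without matching event capture would bias rates downward. Counting from the later of index and entry is standard delayed-entry handling.

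**Effectiveness runs from index while safety may start later.** A reader might see an inconsistency. The difference follows from the data: historic clinical measurements are collected at entry (Table 8.1.1.1, footnote b), whereas adverse events are reported from consent.

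**The protocol makes no claim about starters.** True. It speaks of long-term safety during the Registry, and the pooled rate is a valid description of that. This is why the remedy is partly a matter of labelling.

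**The split belongs in the SAP.** This stands in part. Section 18.1 leaves full details to the SAP, 18.1.4 allows summaries accounting for time where applicable, and 18.1.8 lets the SAP prevail. The protocol does not say that only one pooled rate will be given, and it does not tie the exposure-adjusted rates to hypersensitivity by name. But the protocol itself fixes the population and the window, and it lists the dimensions of the hypersensitivity summary without either split.

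**The Substudy analyses recover early data.** Only for MOR-005 and MOR-007 Substudy patients, and in separate analyses. The 24 weeks of MOR-004 are not expressly included.

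**Conclusion.** The point holds as a limit on interpretation that is cheap to remove. It is not an error in the window or the population. The pooled rate describes on-registry experience. It describes risk after starting treatment only if the hazard is constant over time on drug, and the Objective 5 safety analysis inherits the same limit.

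The 62-94% rests on an assumed early hazard 5 to 10 times the later one, on 20-80% of person-time coming from established users, and on all of those users being past 6 months. Some may not be: the expanded access programme ran only from June 2013 to March 2014. At a ratio of 2 the range is 93-98%, and with a constant hazard there is no bias.

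Two stronger readings are not supported:
- **That pooling hides most of the early risk.** In the model of step 2 the pooled rate is 12-26% of the first-6-month rate. Most of that gap is 5-year averaging: a pure new-user cohort already gives 1.4/5 = 28% or 1.9/10 = 19%.
- **That the population is mainly established users.** The documents do not give the mix.

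**What to change.** Keep the window and the pooled rate. In Objective 2, with the same wording carried into Objective 5:

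- label the pooled rate as on-registry experience in a mixed population of new and prevalent users;
- report hypersensitivity, anaphylaxis and infusion-related adverse event rates by time since index, for example 0-6 months, 6-12 months, 1-2 years and over 2 years;
- report them separately for patients with index on or after Registry Entry and patients with index before it;
- state that person-time runs over the same interval as the counted events.

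No back-collection of events is needed. Index and event dates are already required for the planned analyses, and Objective 1 already stratifies by ERT status at entry, which is much the same split. The cost is a few sentences in the protocol and SAP and some table rows. The downside is fewer events per cell and wider intervals, which is tolerable in a study with no powered hypothesis (18.1.2).

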# **18.1.2** Sample Size Determination

All MPS IVA patients will be invited to enrol in the Registry, assuming all regulatory requirements are met for sites that have agreed to participate, in countries where marketing authorisation has been granted.

The sample size of the study is not determined by statistical power consideration, as no statistical hypotheses are posed.

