# 18.1.4 General Analysis Considerations

Descriptive summaries of continuous variables will include the mean, SD, median, range, and 95% confidence interval and/or inter-quartile range when appropriate. Descriptive summaries of categorical variables will include n and percent. When possible/applicable graphical summary statistics over time and/or summary statistics accounting for time will be utilized.

Statistical tests will be two-sided at the 0.05 level, unless otherwise specified. All confidence intervals will be two-sided 95% confidence intervals, unless otherwise specified. All statistical tests and associated p-values will be considered nominal. See Section 11.1 for definitions of timepoints.

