# 22 MANAGEMENT AND REPORTING OF ADVERSE EVENTS/ADVERSE REACTIONS

# 22.1 Safety Parameters and Definitions

Investigators are requested to report the following AEs/ARs that are considered important for the evaluation of Vimizim safety and ongoing risk-benefit assessments. Report the following to the sponsor within 1 business day:

- All AEs, regardless of causality, occurring within 24 hours of Vimizim infusion (refer to the definition of a hypersensitivity reaction temporally-related to a Vimizim infusion below);
- All SAEs occurring in patients administered at least 1 dose of Vimizim, regardless of causal attribution (refer to SAE definition);
- All non-serious ARs to Vimizim (refer to AR definition);
- All occurrences of spinal cord compression in patients participating in the Registry or the Registry Substudies as SAEs, whether Vimizim was administered or not; and
- Any pregnancy that occurs in a patient administered Vimizim;
- Unusual Failure in Efficacy: a situation where Vimizim fails to produce the expected intended effect, which may result in an adverse outcome for the patient, including an exacerbation of the condition for which the product is being used.

Non-serious AEs, other than those occurring within 24 hours of Vimizim infusion, that are considered related to the underlying disease and unrelated to Vimizim administration by Investigators do not require reporting for this Registry or the Registry Substudies due to the profusion of expected AEs caused by MPS IVA. In addition, SAEs occurring in patients that have never received Vimizim do not require reporting for this Registry or the Registry Substudies, with the exception of spinal cord compression as stated above.

Stable chronic conditions that are present prior to Registry or Registry Substudy entry that do not worsen should be documented in the patient's medical record. A pre-existing condition should be assessed as an AE if the frequency, intensity, or the character of the condition worsens during participation in the Registry or Registry Substudies and meets one of the criteria above for safety reporting.

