# 23.3 Adverse Event Reporting Instructions

Investigators will promptly record all solicited or patient-reported AEs and SAEs on the Registry AE eCRF.

All SAEs, non-serious ARs, hypersensitivity reactions, pregnancies in patients receiving Vimizim, and all occurrences of spinal cord compression (whether Vimizim was administered or not) will be entered on the AE eCRF and submitted to BPV within 1 business day of learning of the event.

Relevant follow-up information will be entered into the EDC system on the AE eCRF and submitted to BPV as soon as it becomes available and/or upon request.

If the EDC system is not available, all SAEs, non-serious ARs, hypersensitivity reactions, pregnancies in patients receiving Vimizim, and all occurrences of spinal cord compression should be reported to BPV by completing the Registry AE/SAE form, and faxing or emailing the completed report to BPV within 1 business day of learning of the event. Fax or email the report to:

[figure not shown]
**BPV AE [contact]

**BPV email:** [contact]

If any questions arise regarding safety reporting, please contact BPV directly at:

**[contact]

Proprietary and Confidential

Page 72

Investigators are encouraged to contact the Registry medical monitor if deemed necessary to discuss patient safety. Contact information for the medical monitor is as follows:

Name: [name] Address: [name]

[name]

US

**[contact] **Email:** [contact]

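### Total and not-related AE figures will be understated: Section 22.1 leaves many non-serious AEs uncollected outside 24 h of an infusion, but Section 18.1.7 summarises AEs over all on-treatment time

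*Protocol*

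**What the plan says.** **Collection.** Protocol Section 22.1 (with essentially the same list in footnote o of Table 8.1.1.1) asks for three main classes of event in treated patients:
- "All SAEs occurring in patients administered at least 1 dose of Vimizim, regardless of causal attribution", with no time limit;
- "All AEs, regardless of causality, occurring within 24 hours of Vimizim infusion";
- all non-serious adverse reactions, that is, events judged causally related, with no time limit.

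Other non-serious AEs outside the 24 h, if considered disease-related and unrelated to Vimizim, "do not require reporting for this Registry or the Registry Substudies due to the profusion of expected AEs caused by MPS IVA".

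**Analysis.** Section 18.1.7, Objective 2, plans "summarising the incidences of AEs by System Organ Class, Preferred Term, relationship to Vimizim, and severity in the Safety Population". It adds: "Exposure-adjusted incidence rates and event rates while on treatment will be included as part of long-term safety evaluation". Section 18.1.5.3 defines on-treatment time as the infusion date plus 7 days.

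**Caveats.** Section 18.1.7 does not restrict these summaries to the classes collected throughout. Section 20 (limitations) mentions that recommended assessments may be incomplete, then refers to Section 22 for AE reporting. It does not say that AE collection is selective.

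**Recording instruction.** Section 23.3 says: "Investigators will promptly record all solicited or patient-reported AEs and SAEs on the Registry AE eCRF". Read alone, this is wider than Section 22.1.

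**The concern.** Whether a non-serious AE enters the database depends on two things: how long after an infusion it occurred, and whether the investigator thought it related. The analysis then tabulates AEs by relationship and divides by person-time that counts every day of the week. For the exempt class, the numerator covers about one day per infusion and the denominator covers seven. The relationship table has already been filtered on relationship before it is drawn up.

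The protocol's own reason for the exemption is that such events are expected in profusion, so the uncollected class is large by its own account. Long-term safety is a stated objective of this post-authorisation safety study. A reader of the tables would take the all-AE rate as the rate of AEs on treatment, and the related share as the proportion of AEs due to the drug. Neither reading would be right, and nothing in the protocol warns of it.

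**Working it through.** The protocol states no AE rate, event count or expected related share, so there is no figure to reproduce. The arithmetic below is an illustration.

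**Inputs from the protocol**
- Collection window: 24 h (Section 22.1 list). The definition in Section 22.1 of a reaction temporally related to an infusion runs from the start of the infusion to 1 day after its end. With a 4 h infusion (Table 6.1.1) that is 28 h.
- Time at risk: 7 days = 168 h per infusion (Section 18.1.5.3).

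**Assumptions**
- Weekly infusions. This is the main trial regimen in Table 6.1.1; the registry does not fix a schedule.
- Non-serious AEs only. SAEs are left out.
- Related non-serious events are fully captured, as Section 22.1 requires. Unrelated ones are captured only in the window.
- c = event rate inside the window relative to outside: 1, 2 or 5.
- r = true related share of non-serious AEs: 10% or 20%.

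**Formulas**
- Window share: w = 24/168 = 14.3%, or 28/168 = 16.7%.
- Captured share of unrelated non-serious AEs: k = c·w / (c·w + 1 − w).
- Understatement of their rate: 1/k.
- Related share shown: r / (r + (1 − r)·k).

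| Window | c | k | Understatement | Shown if r = 10% | Shown if r = 20% |
|---|---|---|---|---|---|
| 24 h | 1 | 14.3% | 7.0-fold | 43.8% | 63.6% |
| 24 h | 2 | 25.0% | 4.0-fold | 30.8% | 50.0% |
| 24 h | 5 | 45.5% | 2.2-fold | 19.6% | 35.5% |
| 28 h | 1 | 16.7% | 6.0-fold | 40.0% | 60.0% |
| 28 h | 2 | 28.6% | 3.5-fold | 28.0% | 46.7% |
| 28 h | 5 | 50.0% | 2.0-fold | 18.2% | 33.3% |

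Example, 24 h window, c = 1, r = 10%: 0.10 / (0.10 + 0.90 × 0.143) = 43.8%.

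**All non-serious AEs together.** The captured fraction is r + (1 − r)·k. For r = 10% and 24 h it is 22.9% at c = 1 (1/0.229 = 4.4-fold understatement) and 50.9% at c = 5 (2.0-fold).

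**If incidence means patients with at least one event**, the loss is smaller where events are frequent. Take Poisson counts, even spread and m expected exempt-type events per patient. The true incidence is 1 − exp(−m) and the reported incidence is 1 − exp(−m·w).
- m = 2: 86.5% true, 24.9% (24 h) or 28.3% (28 h) reported.
- m = 10: about 100% true, 76.0% or 81.1% reported.

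**Classes collected throughout.** For SAEs and related non-serious reactions the captured share required by Section 22.1 is 1, so the reporting rule leaves their rates over on-treatment time unchanged.

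**The case against.** **Selective collection is legitimate.** Section 22.1 adopts it openly and gives a reason, and the study is descriptive: "The sample size of the study is not determined by statistical power consideration, as no statistical hypotheses are posed". This stands. The rule itself is not the defect; summarising its output as though collection were complete is.

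**The outcomes that matter are intact.** A reader might infer that all AE incidences and exposure-adjusted rates are wrong by construction. The documents do not support that. SAEs of any causality and all non-serious adverse reactions are collected without a time limit, and every AE within 24 h of an infusion is collected. The serious hypersensitivity and anaphylaxis outcomes named in Objective 2 fall in these classes. Section 18.1.7 also plans separate summaries of hypersensitivity, anaphylaxis and infusion-related events.

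**The size is soft.** This also stands. The 6- to 7-fold figure needs weekly infusions and events spread evenly over the week. The planned table includes SAEs, so its related share would differ from the one shown above. A patient-level incidence loses less than an event rate. The figures also apply only to the exempt class: a non-serious AE outside the window and unrelated to both drug and disease is not on the required list, yet the exemption does not literally cover it.

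**The SAP may settle the rate classes.** Section 18.1 leaves full details to the SAP and Section 18.1.8 lets the SAP prevail. Section 18.1.7 does not say which classes receive exposure-adjusted rates. But it does fix the AE summary by relationship and severity without restriction, and no SAP can recover events that were never collected.

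**Section 23.3 is loose wording.** A reader might infer that sites are under conflicting orders and that capture will differ between them. Sections 23.1 and 23.2 tie recording to the events described in Section 22 and to reportable events, which largely resolves it. Different capture between sites is conjecture. The sentence still deserves tidying.

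**Conclusion.** The point holds in a limited form, at moderate severity. If Section 18.1.7 is followed as written, four outputs are distorted in a known direction. The all-AE total and its exposure-adjusted rate, the not-related non-serious rows and the lower-severity rows are too low; the share of AEs attributed to Vimizim is too high. The direction follows from the reporting rule alone, provided sites apply it and some exempt events occur outside the window.

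The size rests on assumptions the protocol does not supply: a weekly schedule, how events cluster after infusion, and the true related share. Over the range examined, event rates of the exempt class are understated about 2-fold to 7-fold. A true related share of 10% among non-serious AEs appears as about 20% to 44% with the 24 h window, or 18% to 40% with 28 h. Figures for SAEs, related adverse reactions and infusion-window events are sound.

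**What to change.** 1. **Section 18.1.7, Objective 2.** Limit exposure-adjusted rates to the classes collected throughout: SAEs, and non-serious adverse reactions, each per on-treatment person-time.
2. **Same section.** Report all-causality non-serious AEs only for the 24 h infusion window, on matching time at risk. A per-infusion denominator can be used where doses are recorded, but it is not assured: Section 18.1.1 says only that treatment information may be recorded, and Section 11.11 asks for duration and dose changes.
3. **Same section.** Do not present an all-AE exposure-adjusted rate, or a related/not-related split of non-serious AEs outside the window. Label any overall table *reportable AEs (Section 22.1)*.
4. **Section 20.** State that AE collection is selective, and which figures it affects.
5. **Section 23.3.** Restrict the recording sentence to *all reportable AEs (Section 22.1)*.

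The cost is protocol and SAP wording and table shells, with no new data collection. The downside is that there will be no single overall AE rate.
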